10.6 Management of adverse events for AEs associated with olaparib

Any toxicity observed during the course of the study could be managed by interruption of the dose of study treatment or dose reductions. Repeat dose interruptions are allowed as required, for a maximum of 4 weeks on each occasion. If the interruption is any longer, the study team must be informed. Study treatment can be dose reduced to 250 mg twice daily as a first step and to 200 mg twice daily as a second step. If further reduction is required, treating invesigators should follow the SOC use for Olaparib. If patient is clinically benefiting from prior POLAR treatment, patient can continue to receive pembrolizumab alone or olaparib alone depending on the specific toxicity related to one of these agents. Once dose is reduced, escalation is not permitted (except following concomitant treatment with CYP3A4 inhibitors – see Section 6.5

10.6.1 Management of hematological toxicity associated with olaparib

10.6.1.1 Management of anemia associated with olaparib

Table 7. Management of anemia

Hemoglobin	Action to be taken
Hb < 10 but ≥ 8 g/dl (CTCAE Grade 2)	First occurrence:
	Give appropriate supportive treatment and investigate causality.
	Investigator judgement to continue olaparib or combination treatment with supportive treatment (e.g. transfusion) or interrupt dose for a maximum of 4 weeks. Study treatment can be restarted if Hb has recovered to > 8g/dl.
	Subsequent occurrences:
	If $Hb < 9$ but ≥ 8 g/dl, dose interrupt (for max of 4 weeks) olaparib or combination until $Hb \ge 9$ g/dl and upon recovery dose reduction may be considered (to 250 mg twice daily as a first step and to 200 mg twice daily as a second step).
Hb < 8 g/dl (CTCAE Grade 3)	Give appropriate supportive treatment (e.g. transfusion) and investigate causality.
	Interrupt olaparib or combination treatment for a maximum of 4 weeks until improved to $Hb \ge 8$ g/dl.
	Upon recovery dose reduce to 250 mg twice daily as a first step and to 200 mg twice daily as a second step in the case of repeat Hb decrease.

^{**}Please note, if Hb < 8 g/dl, Hb needs to recover to ≥ 8 g/dl to resume with a reduced dose.

Common treatable causes of anemia (e.g., iron, vitamin B12 or folate deficiencies and hypothyroidism) should be investigated and appropriately managed. In some cases, management of anemia may require blood transfusions. For cases where patients develop prolonged hematological toxicity (≥2-week interruption/delay in study treatment due to CTC grade 3 or worse anemia and/or development of blood transfusion dependence), refer to guidance later in this section for the management of this.

10.6.1.2 Management of neutropenia, leukopenia and thrombocytopenia associated with olaparib

Table 8. Management of neutropenia, leukopenia and thrombocytopenia

Toxicity	Study treatment dose adjustment
CTCAE Grade 1-2	Investigator judgement to continue treatment or if dose interruption, this should be for a maximum of 4 weeks; appropriate supportive treatment and causality investigation
CTCAE Grade 3-4	Dose interruption until recovered to CTCAE G 1 or better for a maximum of 4 weeks. If repeat CTCAE G 3-4 occurrence, dose reduce olaparib to 250 mg twice daily as a first step and 200 mg twice daily as a second step

Adverse event of neutropenia and leukopenia should be managed as deemed appropriate by the investigator with close follow up and interruption of study drug if CTC grade 3 or worse neutropenia occurs.

Primary prophylaxis with granulocyte colony-stimulating factor (G-CSF) is not recommended, however, if a patient develops febrile neutropenia, study treatment should be stopped and appropriate management including G-CSF should be given according to local hospital guidelines. Please note that G-CSF should not be used within at least 24 h (7 days for pegylated G-CSF) of the last dose of study treatment unless absolutely necessary.

Platelet transfusions, if indicated, should be done according to local hospital guidelines.

For cases where patients develop prolonged hematological toxicity (≥2-week interruption/delay in study treatment due to CTC grade 3 or worse), refer to guidance later in this section for the management of this.

10.6.1.1 Management of prolonged hematological toxicities while on POLAR treatment

If a patient develops prolonged hematological toxicity such as:

- ≥2 week interruption/delay in study treatment due to CTC grade 3 or worse anemia and/or development of blood transfusion dependence
- ≥2 week interruption/delay in study treatment due to CTC grade 3 or worse neutropenia (ANC < 1 x 10⁹/L)
- ≥2 week interruption/delay in study treatment due to CTC grade 3 or worse thrombocytopenia and/or development of platelet transfusion dependence (Platelets < 50 x 10⁹/L)

Check weekly differential blood counts including reticulocytes and peripheral blood smear. If any blood parameters remain clinically abnormal after 4 weeks of dose interruption, the patient should be referred to hematologist for further investigations. Bone marrow analysis and/or blood cytogenetic analysis should be considered at this stage according to standard hematological practice. Study treatment should be discontinued if blood counts do not recover to CTC G 1 or better within 4 weeks of dose interruption.

Development of a confirmed myelodysplastic syndrome or other clonal blood disorder should be reported as an SAE and full reports must be provided by the investigator to Merck Patient Safety. Olaparib treatment should be discontinued if patient's diagnosis of MDS and/or AML is confirmed.

10.6.2 Management of non-hematological toxicity associated with olaparib

Repeat dose interruptions are allowed as required, for a maximum of 4 weeks on each occasion. If the interruption is any longer than this the study monitor must be informed. Where toxicity reoccurs following re-challenge with study treatment, and where further dose interruptions are considered inadequate for management of toxicity, then the patient should be considered for dose reduction or must permanently discontinue study treatment.

Study treatment can be dose reduced to 250 mg twice daily as a first step and to 200 mg twice daily as a second step. If further reduction is required, treating investigators should follow the SOC use for Olaparib. Treatment must be interrupted if any NCI-CTCAE grade 3 or 4 adverse event occurs which the investigator considers to be related to administration of study treatment.

Page | 37

10.6.3 Management of new or worsening pulmonary symptom associated with olaparib

If new or worsening pulmonary symptoms (e.g., dyspnea) or radiological abnormalities occur in the absence of a clear diagnosis, an interruption in study treatment dosing is recommended and further diagnostic workup (including a high-resolution CT scan) should be performed to exclude pneumonitis.

Following investigation, if no evidence of abnormality is observed on CT imaging and symptoms resolve, then study treatment can be restarted, if deemed appropriate by the investigator. If significant pulmonary abnormalities are identified, these need to be discussed with the Study Physician.

10.6.4 Management of nausea and vomiting associated with olaparib

Events of nausea and vomiting are known to be associated with olaparib treatment. These events are generally mild to moderate (CTCAE grade 1 or 2) severity, intermittent and manageable on continued treatment. The first onset generally occurs in the first month of treatment for nausea and within the first 6 months of treatment for vomiting. For nausea, the incidence generally plateaus at around 9 months, and for vomiting at around 6 to 7 months.

No routine prophylactic anti-emetic treatment is required at the start of study treatment; however, patients should receive appropriate anti-emetic treatment at the first onset of nausea or vomiting and as required thereafter, in accordance with local treatment practice guidelines. Alternatively, olaparib tablets can be taken with a light meal/snack (i.e. 2 pieces of toast or a couple of biscuits).

As per international guidance on antiemetic use in cancer patients (NCCN), generally a single agent antiemetic should be considered e.g. dopamine receptor antagonist, antihistamines or dexamethasone.

10.6.5 Interruptions for intercurrent non-toxicity related events associated with olaparib

Study treatment dose interruption for conditions other than toxicity resolution should be kept as short as possible. If a patient cannot restart study treatment within 4 weeks for resolution of intercurrent conditions not related to disease progression or toxicity, the case should be discussed with study physician.

All dose reductions and interruptions (including any missed doses), and the reasons for the reductions/interruptions are to be recorded in the eCRF.

Study treatment should be stopped at least 3 days prior to planned surgery. After surgery study treatment can be restarted when the wound has healed. No stoppage of study treatment is required for any needle biopsy procedure.

Study treatment should be discontinued for a minimum of 3 days before a patient undergoes radiation treatment. Study treatment should be restarted within 4 weeks as long as any bone marrow toxicity has recovered.

Page | 38

Because the AEs related to olaparib may include asthenia, fatigue and dizziness, patients should be advised to use caution while driving or using machinery if these symptoms occur.

10.6.6 Management of renal impairment associated with olaparib

If subsequent to study entry and while still on study therapy, a patient's estimated CrCl falls below the threshold for study inclusion (≥51 ml/min), retesting should be performed promptly.

A dose reduction is recommended for patients who develop moderate renal impairment (calculated creatinine clearance by Cockcroft-Gault equation or based on a 24-hour urine test of between 31 and 50 ml/min) for any reason during the course of the study: the dose of olaparib should be reduced to 200 mg twice daily.

Because the CrCl determination is only an estimate of renal function, in instances where the CrCl falls to between 31 and 50 mL/min, the investigator should use his or her discretion in determining whether a dose change, or discontinuation of therapy is warranted.

Olaparib has not been studied in patients with severe renal impairment (creatinine clearance \leq 30 ml/min) or end-stage renal disease; if patients develop severe impairment or end stage disease is it recommended that olaparib be discontinued.

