POLAR: a phase 2 trial for pembrolizumab and olaparib maintenance for metastatic PDAC and HRD and/or Exceptional Response to Platinum – Ver. 5/3/2020

1

the appropriate dose of pembrolizumab for adults across all indications and regardless of tumor type.

For pharmacological class, please refer to Investigator's Brochure.

5.2 OLAPARIB:

Olaparib (AZD2281, KU-0059436) is a potent inhibitor of poly ADP-ribose polymerase (PARP) developed as a monotherapy as well as for combination with chemotherapy, ionizing radiation and other anti-cancer agents including novel agents and immunotherapy. The approved tradename for olaparib is LYNPARZA. Since 2012, the tablet formulation was designed to deliver the therapeutic dose of olaparib in fewer dose units than the capsule.

Active Ingredients and pharmacological class:

Chemical Name: 4-[(3-{[4-(cyclopropylcarbonyl)piperazin-1-yl]carbonyl}-4-fluorophenyl)methyl]phthalazin-1(2H)-one.

Dose formulation and storage:

Olaparib is presented for po administration as a green, film-coated tablet containing 25 mg, 100 mg or 150 mg of drug substance. The 100 mg strength is also available as a yellow, film-coated tablet. Olaparib tablets are supplied in high-density polyethylene (HDPE) bottles containing desiccant.. Bottles are secured with a child-resistant closure; induction-sealed membranes provide tamper evidence.

The planned dose of olaparib for this study is at a dose of 300 mg orally twice daily (bid). Olaparib is available as a green film-coated tablet containing 150 mg or 100 mg. The planned dose of 300 mg bid will be made up of two x 150 mg tablets bid with 100 mg tablets used to manage dose reductions.

Olaparib will be supplied by Merck. Co. LTD. through their collaboration with AstraZeneca.

Refer to the Investigator's Brochure for Preclinical and Clinical data.

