- Variants of unknown significance (VUS) or benign polymorphisms of above 17 HR-genes from Cohort A and B are considered non-pathogenic and will be excluded from cohort A or B. However, if the participant demonstrates platinum sensitivity, patient can be considered eligible for Cohort C.
- 3. A recurrence after curative surgery is eligible if the recurrence is > 6 months after the last date of adjuvant therapy and the participant has at least stable or responding disease on platinum therapy and meet the above genomic or platinum sensitivity criteria.
- Eastern Cooperative Oncology Group (ECOG) performance status 0-2 (Appendix 1: ECOG)
- 5. Patients must have normal organ and bone marrow function measured within 28 days prior to administration of study treatment as defined as below:
 - Absolute neutrophil count (ANC) ≥1500/µL
 - Hemoglobin ≥9.0 g/dL or ≥5.6 mmol/La
 - Platelets ≥100 000/µL

POLAR: a phase 2 trial for pembrolizumab and olaparib maintenance for metastatic PDAC and HRD and/or Exceptional Response to Platinum – Ver. 5/3/2020

•

2

- Total bilirubin ≤ 2 x ULN
- AST (SGOT) and ALT (SGPT) ≤2.5 × ULN (≤5 × ULN for if liver metastases)
- Creatinine ≤2 x ULN
- 6. Patients with measurable disease and/or non-measurable or no evidence of disease assessed at baseline by CT (or MRI where CT is contraindicated) are eligible.
- 7. Postmenopausal or evidence of non-childbearing status for women of childbearing potential: negative urine or serum pregnancy test. Postmenopausal is defined as:
 - Amenorrhoeic for 1 year or more following cessation of exogenous hormonal treatments
 - Luteinizing hormone (LH) and Follicle stimulating hormone (FSH) levels in the postmenopausal range for women under 50
 - Radiation-induced oophorectomy with last menses >1 year ago
 - Chemotherapy-induced menopause with >1-year interval since last menses
 - Surgical sterilization (bilateral oophorectomy or hysterectomy)

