- c. Has a known history of active TB (Bacillus tuberculosis).
- 11. Any prior treatment with any PARP inhibitor, including olaparib.
- Any previous treatment with any anti-PD-1, anti-PD-L1, or anti-PD-L2 agent.
- 13. Has received systemic therapy 2 weeks prior to starting treatment
- 14. Patients with any recent investigational agents are not eligible unless at least 2 weeks or 5 half-lives of investigational agent prior to the first dose of study treatment have passed.
- 15. Live vaccines within 30 days prior to the first dose of study treatment and while participating in the study are not permitted. Examples of live vaccines include, but are not limited to, the following: measles, mumps, rubella, varicella/zoster, yellow fever, rabies, BCG, and typhoid vaccine. Seasonal influenza vaccines for injection are generally killed virus vaccines and are allowed; however, intranasal influenza vaccines (e.g., FluMist®) are live attenuated vaccines and are not allowed.
- 16. Active autoimmune disease that has required systemic treatment in the past 2 years is not permitted (i.e. with use of disease modifying agents, corticosteroids or immunosuppressive drugs). Replacement therapy (e.g., thyroxine, insulin, or physiologic corticosteroid replacement therapy for adrenal or pituitary insufficiency, etc.) is not considered a form of systemic treatment.
- 17. Palliative radiotherapy must have been completed 14 or more days before Cycle 1 Day 1.

- 18. If participant received major surgery within 4 weeks before screening, they must have recovered adequately from the toxicity and/or complications from the intervention prior to starting study treatment.
- 19. Participants must have recovered from all AEs due to previous therapies to ≤Grade 1 or baseline. Participants with ≤Grade 2 neuropathy may be eligible. Participants with ≤Grade 2 alopecia may be eligible as well.
- 20. Concomitant use of known strong CYP3A inhibitors (e.g. itraconazole, telithromycin, clarithromycin, protease inhibitors boosted with ritonavir or cobicistat, indinavir, saquinavir, nelfinavir, boceprevir, telaprevir) or moderate CYP3A inhibitors (e.g. ciprofloxacin, erythromycin, diltiazem, fluconazole, verapamil). The required washout period prior to starting is 2 weeks.

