10.0 TREATMENT/INTERVENTION PLAN

10.1 Administration

Within 4 weeks of screening date, eligible patients will receive combination pembrolizumab and olaparib as maintenance therapy until clinical or radiographic progression or discontinuation due to -limiting toxicity. If a patient requires discontinuation of either olaparib or pembrolizumab for reasons of toxicity and if in the opinion of the treating MD the patient is continuing to derive benefit, the patient is able to continue on study. Additionally, in the absence of unacceptable toxicity, participants who meet criteria for disease progression per RECIST 1.1 while receiving treatment will be permitted to continue treatment, if in the opinion of the treating MD the patient is continuing to derive benefit from the treatment. iRECIST will be used to evaluate the objective response rate and the co-primary endpoint of overall response rate will be assessed by RECIST v1.1. (Section 12.0 CRITERIA FOR REMOVAL FROM STUDY).

The POLAR treatment will be administered to subjects as outlined in Figure 1 - Schematic treatment and biospecimen collection schedule. Approximately within 4 weeks of screen visit, patient will get baseline biopsy and will start the first dose pembrolizumab 200 mg IV every 3 weeks and olaparib 300 mg twice daily orally. After the first 6 months (9 cycles), on C10D1 Pembrolizumab 400 mg IV every 6 week plus olaparib 300 mg twice a day orally will be continued. Per treating investigator's discretion, patients may remain at Pembrolizumab 200 mg IV every 3 weeks after the first 9 cycles. Additionally, to accomodate patients traveling far distances, if, per treating investigator, after the first or second imaging, there are no toxicities, patient's dosing of Pembrolizumab may change to 400 mg IV every 6 weeks. All cycles will be 21 days (3 weeks) in length. Subjects will be monitored for toxicity every three weeks for the first 9 cycles, and every six weeks thereafter, unless clinically indicated to be monitored every 3 weeks.

Table 2. Trial treatment (POLAR)

Drug	Dose	Dose Frequency	Route of Administration	Treatment Period	Use
Pembrolizumab	200 mg	Q3W	IV infusion	Day 1 of each 3- week cycle for cycle 1-9	experimental
Pembrolizumab	400mg	Q6W	IV infusion	Day 1 of every even cycle beginning with Cycle 10	experimental
Olaparib	300 mg (two 150 mg)	BID	Orally	Daily continuously	experimental

The following parameters must be acceptable prior to initiation of protocol treatment:

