10.7 Dose modification and toxicity management for AEs associated with olaparib

Dose Reductions

For guidance on dose reductions when concomitant strong or moderate CYP3A inhibitors cannot be avoided see below Table 6 and Table 7.

When dose reduction is necessary patients will take one 150 mg tablet and one 100 mg tablet twice daily or two x 100 mg tablet twice daily, or one 150 mg tablet twice daily or one 100 mg tablet twice daily. If further reduction is required, treating investigators should follow the SOC use for Olaparib.

In case a dose reduction is necessary, the Study treatment will be administered as follows:

Table 5. Dose reductions for study treatment to manage adverse events

Initial Dose	Following re-challenge post interruption: Dose reduction 1	Dose reduction 2*
300 mg twice daily	250 mg twice daily	200 mg twice daily
(Two 150 mg tablets)	(150 mg tablet and 100 mg tablet)	(Two 100 mg tablets)

^{*}If further reduction is required, treating investigators should follow the SOC use for Olaparib.

Table 6. Dose reduction for study treatment if patient develops moderate renal impairment

Initial Dose	Moderate renal impairment (calculated creatinine clearance by Cockcroft -Gault equation or based on a 24-hour urine test between 31 and 50 ml/min): Dose reduction	
300 mg twice daily	CrCl 51 to 80 mL/minute: No dosage adjustment necessary.	
	CrCl 31 to 50 mL/minute: Reduce dose to 200 mg twice daily.	
	CrCl ≤30 mL/minute: There are no dosage adjustments provided in the manufacturer's labeling (has not been studied).	
	End-stage renal disease: There are no dosage adjustments provided in the manufacturer's labeling (has not been studied).	

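### Section 10.6.6 relies on a CrCl ≥51 mL/min entry threshold that the eligibility criteria do not contain, and no rule adjusts the 300 mg twice-daily olaparib starting dose for a patient who enters below it

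*Protocol*

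**What the plan says.** Section 10.6.6 of the protocol sets the response to declining renal function on olaparib. It applies when a patient's "estimated CrCl falls below the threshold for study inclusion (≥51 ml/min), retesting should be performed promptly". The clause treats a creatinine clearance of at least 51 mL/min as a condition of entry.

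The entry conditions themselves are in three places:

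- Section 6.1, criterion 5, gives one renal requirement: "Creatinine ≤2 x ULN".
- Section 10.1 repeats that limit in a list introduced by "The following parameters must be acceptable prior to initiation of protocol treatment".
- Section 6.2 has no renal criterion. The nearest item is exclusion 19: "Participants must have recovered from all AEs due to previous therapies to ≤Grade 1 or baseline".

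The starting dose is the same for all. Section 5.2 and Table 2 give olaparib 300 mg twice daily, and Section 10.1 says the patient "will start the first dose pembrolizumab 200 mg IV every 3 weeks and olaparib 300 mg twice daily orally". None of the three makes a renal exception.

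The renal dose rules concern later change. Table 6 in Section 10.7 is titled "Dose reduction for study treatment if patient develops moderate renal impairment" and includes the row "CrCl 31 to 50 mL/minute: Reduce dose to 200 mg twice daily". Section 10.6.6 recommends the same reduction for moderate impairment arising during the study, then leaves a dose change or discontinuation at CrCl 31–50 to the investigator's discretion. For severe impairment (CrCl ≤30) that develops, it recommends stopping olaparib and notes that the drug has not been studied there.

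**The concern.** Section 10.6.6 is written as if screening had already removed everyone below 51 mL/min. If screening does not do that, two gaps open together. Patients with moderate or even severe impairment can meet the written criteria. The renal dose rules, which speak of impairment that develops or of clearance that falls below the entry level, do not literally reach a patient who was already there at baseline.

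What is at stake is dosing safety from the first tablet. An eligible patient could start at 300 mg twice daily with a clearance at which the protocol would recommend 200 mg twice daily, or no olaparib, had the same clearance been reached on treatment. An investigator who relies on Section 10.6.6 may also believe that the eligibility checklist has covered this.

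**Working it through.** **1. Does the threshold exist?** The lists in Sections 6.1 and 10.1 agree with each other. Both give creatinine ≤2 × ULN and neither mentions clearance. Section 6.2 contains no clearance limit. The phrase about normal organ function in criterion 5 is defined by its list, so it adds nothing. The figure of 51 mL/min as an entry threshold appears only in Section 10.6.6.

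**2. Does creatinine ≤2 × ULN imply CrCl ≥51?** Section 10.6.6 and Table 6 name the Cockcroft-Gault equation:

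CrCl = (140 − age) × weight in kg ÷ (72 × serum creatinine in mg/dL), multiplied by 0.85 for women.

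The protocol gives no ULN. Assumed: 1.2 mg/dL for men (range 1.1–1.3) and 1.0 mg/dL for women (range 0.9–1.1). Ages and weights are illustrative; Sections 6.1 and 6.2 set no upper age or lower weight limit.

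With creatinine exactly at ULN:

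| Profile | Calculation | CrCl (mL/min) | Over the ULN range |
|---|---|---|---|
| Man, 65 y, 70 kg | 75 × 70 ÷ (72 × 1.2) | 60.8 | 56.1–66.3 |
| Man, 75 y, 70 kg | 65 × 70 ÷ (72 × 1.2) | 52.7 | 48.6–57.4 |
| Woman, 65 y, 60 kg | 75 × 60 × 0.85 ÷ (72 × 1.0) | 53.1 | 48.3–59.0 |
| Woman, 75 y, 55 kg | 65 × 55 × 0.85 ÷ (72 × 1.0) | 42.2 | 38.4–46.9 |

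One profile in four is below 51 throughout the range with a creatinine that is not raised at all. Two others fall below 51 at the upper end of the assumed ULN.

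With creatinine above ULN but within the criterion:

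- Man, 75 y, 70 kg, at 2 × ULN: 65 × 70 ÷ (72 × 2.4) = 26.3. With ULN 1.1 or 1.3 the divisor becomes 72 × 2.2 or 72 × 2.6, giving 28.7 or 24.3.
- Woman, 75 y, 55 kg, at 1.5 × ULN: 42.2 ÷ 1.5 = 28.1 (46.9 ÷ 1.5 = 31.3 to 38.4 ÷ 1.5 = 25.6).

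A wider grid (ages 50, 60 and 70; a woman of 60 kg, men of 70 and 80 kg; ULN 1.0–1.3 mg/dL for either sex) gives CrCl of 19–50 at 2 × ULN, below 51 in every case. On the same grid, CrCl equals 51 at a creatinine between 0.75 and 1.96 × ULN. So the creatinine limit does not imply the clearance threshold on any of these profiles.

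**3. Which dose does such a patient get?**

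| CrCl | If reached on study | If present at entry |
|---|---|---|
| 31–50 | 200 mg twice daily recommended, investigator discretion (Table 6, Section 10.6.6) | 300 mg twice daily (Sections 5.2 and 10.1, Table 2) |
| ≤30 | Discontinuation recommended (Section 10.6.6) | 300 mg twice daily (same places) |

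**4. Does exclusion 19 close the gap?** It concerns unrecovered adverse events of previous therapies and also accepts return to baseline. It can remove some patients with a treatment-related creatinine rise. It does not act on low clearance at a normal creatinine, nor on impairment that predates treatment.

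**The case against.** The case for leaving the text alone has real content.

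- A starting dose is specified. A reader might infer from the missing threshold that the protocol gives no starting dose below 51 mL/min. It does not support that: 300 mg twice daily is fixed for everyone. Only the renal adjustment at entry is missing.
- Renal function is monitored. Table 1 includes creatinine, and Table 9 schedules the chemistry panel at screening, in cycles 1 to 9 and in even cycles from cycle 10. Section 11.1 asks for treatment-day assessments before the infusion. An investigator would therefore have the creatinine before treatment and could apply the Table 6 bands early. This stands as mitigation, but nothing requires clearance to be calculated or acted on at baseline.
- At CrCl 31–50 the protocol only recommends 200 mg and then defers to the investigator, so 300 mg is not forbidden there even on study. A reader might infer that any such patient is being dosed in breach of the protocol; the discretion clause does not support that. The discrepancy is sharper at ≤30, which in the profiles above needs a creatinine above ULN.
- The profiles are assumed. At the central ULN values and creatinine at ULN, three of the four are above 51. The examples show that entry below 51 is possible, not how common it would be.

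None of this supplies the missing criterion.

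**Conclusion.** Wrong as written. Section 10.6.6 cites an inclusion threshold of CrCl ≥51 mL/min that Sections 6.1, 6.2 and 10.1 do not contain. The criterion they do contain admits patients below it. For those patients no rule adjusts the 300 mg twice-daily starting dose, because Table 6 and Section 10.6.6 are worded for impairment that develops on study.

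The textual mismatch rests on no assumption. The clearances rest on assumed ULN, age and weight: about 42 mL/min (38–47) for a 75-year-old, 55 kg woman with creatinine at ULN, and about 26 (24–29) for a 75-year-old, 70 kg man at twice ULN. How many of the planned 63 patients would be affected cannot be derived.

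This is a safety and eligibility inconsistency. A reader might infer that it weakens the efficacy conclusions, but it changes no endpoint definition, sample size or error rate.

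**What to change.** One of two amendments; the choice is clinical.

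(a) Add CrCl ≥51 mL/min, by Cockcroft-Gault or 24-hour urine, to Section 6.1 criterion 5 and to the pre-dose list in Section 10.1. Section 10.6.6 then reads correctly as it stands.

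(b) Remove the reference to an inclusion threshold from Section 10.6.6 and apply the Table 6 bands at entry: start at 200 mg twice daily for CrCl 31–50, and exclude patients at ≤30. Sections 5.2 and 10.1 and Table 2 would need the matching exception to the 300 mg start. No new reduction steps are needed, since Section 10.7 already refers doses below 200 mg to standard-of-care use.

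Neither needs a new test: creatinine and weight are already collected at screening (Tables 1 and 9). The cost is one amendment, and that some patients are excluded under (a) or start at a lower dose, with those at ≤30 excluded, under (b).
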